PROTOCOL

Pilot Clinical Trial on the Effects of Dietary Fibres on Gut Microbiome and Metabolic Profiles in a Transgenerational Cohort

Table of Contents

- 1. Introduction
- 2. Study Hypothesis
- 3. Study Aim
- 4. Primary Outcome
- 5. Secondary Outcomes
- 6. Study Methodology
- 7. Intervention Products
- 8. Study Design
- 8.1 Participants' Recruitment
- 9. Study Design
- **10. Statistical Analysis**
- 11. Withdrawal Criteria and Adverse Events
- 12. Regulatory Issues
- **13. Publication Policy**
- 14. References

1. Introduction:

Westernised diets, rich in animal proteins and fats and low in dietary fibres, have become more common around the world in the past 3-4 decades¹. This trend has been accompanied by a rise in cardiometabolic conditions (diabetes, obesity, heart disease) as well as allergies. However, no causal relationship between these trends has been proven yet. Dietary fibres are complex plant polysaccharides which reach the colon intact; there they are broken down into smaller molecules, such as short-chain fatty acids by the gut bacteria². Examples of short-chain fatty acids include acetate, propionate or butyrate. These molecules end up in the blood stream where they perform a wide range of significant functions, such as appetite regulation, control of colon cells development etc^{2,3}. Increased intake of dietary fibres which leads to a diverse gut bacteria composition and consequently increased production of short-chain fatty acids is associated with good health². Examples of health benefits include lower risks of heart disease or type 2 diabetes.

The recommended daily intake of dietary fibre is 30g, nonetheless, the average daily intake is around 15-18g^{4,5}. A trend characterised by decreased dietary fibre intake has become more apparent in the past decades in various countries around the world^{5,6}. Younger people tended to consume fewer dietary fibres when compared to older people^{5,6}. Among younger people, dietary fibres were generally replaced with animal fats and proteins.

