We want to investigate this hypothesis in women from 2 or 3 generations in direct link from the same family, such as grandmother, mother and daughter. At birth, mothers transmit gut bacteria to their offspring and therefore the maternal microbiome plays an important role in shaping the early composition of offspring's gut microbiota when compared to fathers. Mother's breast milk also influences the gut microbiome of their offspring in early life. However, there is little information on these maternal influences in the late life of offspring and especially in response to dietary fibre intake. Therefore, we want to determine if there is a transgenerational similarity in gut microbiome composition, metabolic profiles and clinical outcomes in response to 4-week high intake of dietary fibres compared to placebo. This approach (individuals in direct link and female participants across all generations) will allow us to 1) determine if there is a maternal influence on the gut microbiome and responses to dietary fibres of younger generations in late life and 2) have a less heterogenous cohort by focusing on women only which will allow for a better understanding of the data.

2. Study Hypothesis:

We hypothesize that compared to placebo, the dietary fibre intervention will lead to a higher production of short-chain fatty acids by the older generation's gut microbiota when compared to that of the younger generation which will translate into differential responses of gut microbiota composition, glucose, insulin, lipids, gut hormones and inflammatory markers levels.

3. Study Aim:

Investigate the effects of a dietary fibre blend taken over a 4-week period on the production of short-chain fatty acids by the gut microbiota, microbiota composition and health outcomes (glucose, insulin, lipids, gut hormones and inflammatory markers levels) of individuals from 2 or 3 generations in direct link (grandmother, mother and daughter).

4. Primary Outcome:

Comparison of the change in SCFA production from baseline to the end of the intervention between grandmothers, mothers and daughters between dietary fibre intervention and placebo.

5. Secondary Outcomes:

- Comparison of gut microbiota composition from baseline to the end of the intervention between grandmothers, mothers and daughters between dietary fibre intervention and placebo.

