Participants will be asked not to consume any intervention products on the study visit. At the end of study visits 1 and 3, participants will receive 56 sachets of intervention products. At study visits 2 and 4, participants will be asked to bring the empty sachets to assess compliance with the intervention. Throughout the 2 study intervention periods, participants will be asked to complete daily the Intervention Product Reminder sheet whenever they take the intervention product. This will also allow for assessing compliance with the intervention.

Intervention products will be stored in sachets and boxes in the Commonwealth Building of Hammersmith campus, Imperial College London.

8. Participants:

10 duos or trios (20-30 participants) females

Inclusion criteria:

- Any of the following groups of people (in direct descent and from the same family):
 - Grandmother, mother and daughter

- Mother and daughter
- Grandmother and granddaughter
- Age 18-85 (inclusive)
- BMI: 18.5-30 kg/m² (inclusive)
- Considering themselves healthy

Exclusion criteria:

- Intake of antibiotics in the past 3 months and during the study
- Intake of probiotic supplements in the past month and during the study
- Regular intake of laxatives in the past month and during the study
- Subjects with the following conditions:
 - Inflammatory Bowel Disease (IBD)
 - Irritable Bowel Syndrome (IBS)
 - Coeliac Disease
 - Type 12 Diabetes
 - Any type of cancer
 - Autoimmune conditions
 - Conditions that affect the liver
 - Conditions that affect the pancreas
- Subjects who require medical intervention in the coming 3 months
- Smokers
- Shift workers
- Gluten intolerance
- Pregnant and lactating women
- Subjects living in care homes
- had weight changes >5% in the preceding 3 months
- Subjects who are unable to give informed consent by themselves
- Subjects who are currently participating in other clinical trials

Support of number of volunteers:

This is a pilot exploratory study in a new area of research and therefore statistical power calculation is not possible.

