The collected samples (stool, urine and blood) will be analysed for: gut microbiota composition (from stools) through 16S rRNA sequencing and qPCR (quantitative Polymerase Chain Reaction); metabolites produced by the gut microbiota (from stools and urine) thorough NMR (Nuclear Magnetic Resonance), GC-MS (gas chromatography coupled with mass spectrometry), LC-MS (liquid chromatography coupled with mass spectrometry), LC-MS (liquid chromatography coupled with mass spectrometry), blood glucose, insulin, gut hormones (PYY and GLP-1), inflammatory markers (C reactive protein) and lipid levels.

11. Statistical Analysis

Statistical tests, such as ANOVA (Analysis of Variance) and t-tests (paired and unpaired) will be used to compare different groups: study participants groups, dietary fibre groups and placebo groups. Correlation analysis (Pearson and/or Spearman) and linear models will be used to analyse the relationship between gut bacteria taxa, short-chain fatty acids levels, metabolites levels, food diary information and demographics. Statistical significance levels will be p<0.05.

Various platforms will be used to analyse the data. Gut microbiome composition will be analysed using 16S rRNA sequencing on Illumina MiSeq and statistical analyses will be performed in R. Species diversity and richness will be calculated and statistical tests include t-tests and Mann-Whitney U tests, statistical significance p<0.05. Species diversity and richness and their changes from baseline between grandmother, mother and offspring will be compared. Data from placebo and dietary fibre intervention will be compared.

Short-chain fatty acids (SCFA) production from stool samples will be measured using GC-MS (Gas Chromatography coupled with Mass Spectrometry). T-tests (paired and/or unpaired) and ANOVA tests will be used to determine whether there are significant differences in SCFA production between grandmothers, mothers and offspring from baseline to end of intervention. Data from placebo and dietary fibre intervention will be compared. Significance levels will be p<0.05.

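### Section 11 does not commit to a test of the primary contrast, which is the fibre-minus-placebo SCFA change compared between generations of the same families

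*Combined protocol and SAP*

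**What the plan says.** Section 4 defines the primary outcome as "Comparison of the change in SCFA production from baseline to the end of the intervention between grandmothers, mothers and daughters between dietary fibre intervention", with placebo as the comparator. Section 2 gives the direction: "compared to placebo, the dietary fibre intervention will lead to a higher production of short-chain fatty acids by the older" generation's microbiota than by the younger's. Together these ask for a product-by-generation contrast. The Introduction adds a family aim, to "determine if there is a maternal influence on the gut microbiome and responses to dietary fibres of younger generations in late life".

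Section 11 opens with ANOVA and t-tests that "will be used to compare different groups: study participants groups, dietary fibre groups and placebo groups". Its SCFA paragraph says "T-tests (paired and/or unpaired) and ANOVA tests will be used to determine whether there are significant differences in SCFA production" between generations from baseline to end of intervention. The next sentence reads "Data from placebo and dietary fibre intervention will be compared". It names no test and does not mention generation. Linear models appear in Section 11 only for associations among taxa, SCFA, metabolites, diet and demographics.

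The SCFA variable is not named; the Introduction says "Examples of short-chain fatty acids include acetate, propionate or butyrate". Section 8 sets the sample at "10 duos or trios (20-30 participants) females" and, because this is a pilot, gives no power calculation.

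**The concern.** Three choices that decide the primary result are left open.

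- **The contrast.** No sentence in Section 11 forms fibre minus placebo within a woman and then compares it between generations. ANOVA is named without factors.
- **The pairing.** A paired test could pair baseline with end, fibre with placebo, or relatives. No family, period or sequence term is mentioned.
- **The variable.** It could be total SCFA or any single acid.

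If these are settled with the data in hand, the trial may report an answer to a different question, or may estimate the right contrast less precisely than its data allow.

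**Working it through.** The plan states no power, SD or effect size, so there is no figure of its own to reproduce. The check compares the texts and then sizes each permitted reading by simulation.

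**1. Target.** For each woman let D = (end − baseline on fibre) − (end − baseline on placebo). The hypothesis is that mean D is larger in the older generation.

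**2. Readings that fit Section 11.**
- (a) Test D between generations, allowing for family. This answers the question.
- (b) Test D between generations, ignoring family.
- (c) Test the fibre-period change between generations, without placebo.
- (d) Test fibre against placebo separately in each generation.

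**3. Inputs.** From the documents: 10 families (Section 8), a two-period crossover (Section 6) and p<0.05 (Section 11). Assumed, because the documents give none: SD of D = 1; correlation r of D between relatives 0.3, range 0 to 0.5; all families trios; and, for power, generation means 0, 0.5 and 1 SD apart. Model: D = generation mean + family effect (variance r) + residual (variance 1 − r). Simulations used 40,000 trials unless stated.

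**4. Family ignored or included, on D.** A shared family effect cancels between generations. Under the null, the between-generation mean square therefore has expectation 1 − r, while the family-blind error mean square has expectation 1, so the test is conservative. With family blocks the noncentrality is 10 × (0.25 + 0 + 0.25)/(1 − r) = 5/(1 − r) on 2 and 18 df. At r = 0.3 this is 7.1, which gives 58.7% power.

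| r | Family ignored: error / power | Family blocks: error / power | Model in the fix: error / power |
|---|---|---|---|
| 0 | 5% / 46% | 5% / 44% | 6% / 45% |
| 0.1 | 4% / 45% | 5% / 48% | 5% / 48% |
| 0.3 | 1.8–1.9% / 42–43% | 5% / 58–59% | 5% / 57% |
| 0.5 | 0.6% / 40% | 5% / 74% | 5% / 72% |

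The last column is REML with sequence included, using within-family df (17) and 8,000 trials. A rerun of 4,000 null trials that used 26 df whenever the family variance was estimated as zero gave errors of 6.3, 5.4, 5.1 and 5.0%. In an assumed mix of 5 trios and 5 duos (25 women), power is 35/34/32/30% with family ignored and 33/35/43/53% with the model.

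**5. Overall fibre test (not the primary outcome).** If 30 women are treated as independent, the variance of the mean is taken as 1/30. In trios it is (1 + 2r)/30, which is 1.6 times larger at r = 0.3. Type I error is 5/7/12/17% at r = 0/0.1/0.3/0.5. A test on family means stays at 5%.

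**6. Reading (d), same true effect in every generation.** Let P be the power within one generation of 10 women. At r = 0, the chance that some generations are significant and others not is 1 − P³ − (1 − P)³. For an effect of 0.7 SD, P = 0.506, so the chance is 1 − 0.130 − 0.120 = 75%. For effects of 0.4–1.0 SD the range is about 41–63% at r = 0.3 and about 35–75% over r = 0 to 0.5.

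**7. Reading (c), generations differing equally on both products.** The true contrast is zero. At r = 0.3 the ANOVA is significant in 2/3/9/42–43% of trials when the oldest and youngest generations differ by 0/0.25/0.5/1 SD of the change.

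**8. Pairing and variable.** Three paired t-tests between relatives on D, each at 5%, give at least one false positive in about 13% of trials at any r. The 25-woman mix has only 5, 6 and 9 such pairs. Testing three acids and their total, each at 5%, gives 10–15% for correlations of 0.8 down to 0.3.

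**The case against.** The strongest reply is that the protocol already states the joined contrast. Section 4 puts change, generation and product in one sentence, and Section 2 gives the direction. The two SCFA sentences in Section 11 are adjacent and can be read together, and an ANOVA can include a product-by-generation term. That stands. A reader might infer that the protocol lacks the contrast or plans a wrong analysis, and the documents support neither. The fault is that Section 11 does not commit to the right reading.

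A reader might also infer that ignoring family produces false positives on the primary contrast. It does the reverse: the test becomes conservative. Inflation arises only in an overall fibre test, and only if relatives share their response.

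Pilot status explains the missing power calculation and limits the consequences. It does not explain an undefined primary test in a randomised crossover with a stated hypothesis and significance level. Blinding until the last visit (Section 7) helps, but nothing fixes the analysis before that date.

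An ordered older-to-younger contrast is tempting as the required primary test. The outcome compares three groups, however, and a contrast on a 0/1/2 generation score has about 2% power if only mothers differ, against 70% for the overall generation test (1 SD, r = 0.3). That choice belongs to the investigators.

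Two things are not missing. Section 12 says data up to withdrawal are used, and Section 8 supplies generation labels. The labels are imperfect, because a mother in a duo may be older than a grandmother in a trio.

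**Conclusion.** The concern holds as under-specification of the primary analysis, and it should be fixed. Readings (c) and (d) comply with Section 11 and do not test the hypothesis. At r = 0.3, (d) gives mixed verdicts in about 41–63% of trials with no true difference between generations. Reading (c) is significant in up to about 42% when a 1 SD generation difference is common to both products. Ignoring family on the right contrast costs about 16 points of power at r = 0.3 in trios (42–43% against 58–59%), about 34 at r = 0.5 (40% against 74%), and nothing at r = 0. These figures illustrate assumed SD, correlation, trend and family structure. The textual gap does not depend on them.

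**What to change.** Before unblinding, replace the SCFA sentence in Section 11 with one primary analysis:

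- Name one SCFA variable, with unit and scale (for example the sum of acetate, propionate and butyrate). Make single acids secondary.
- Compute D for each woman.
- Fit a linear mixed model of D with generation (categorical: grandmother, mother, daughter or granddaughter) and sequence as fixed effects, family as a random intercept, and Satterthwaite degrees of freedom. In a model of D, the sequence term absorbs the period effect. Keep the fitted model if the family variance is estimated as zero.
- Make the generation effect the primary test, two-sided 5%. Report D per generation with 95% confidence intervals.
- Test any overall fibre effect with family as the cluster.

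Two supporting analyses are optional. One is an ordered older-to-younger contrast. The other is a mixed model of change scores that also uses women with only one period. It needs a family-by-product term, because woman and family intercepts alone cancel in D and do not carry a shared response.

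The cost is one paragraph and a few lines of R, which the plan already uses. No data or visits are added. The family variance is imprecise with 10 families: it was estimated as zero in 53/35/11/2% of simulated trio trials at r = 0/0.1/0.3/0.5. If relatives do not share response, the model loses 1–2 points of power and its type I error is about 6%. Adjusting for sequence costs about 2–3 points if there is no period effect. If the two orders differ by 1 or 2 SD of D, omitting it lowers power at r = 0.3 to 45% or 27%, while adjusting holds it at 56–57%.

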- Comparison of metabolic profiles of urine and stool samples from baseline to the end of intervention between grandmothers, mothers and daughters between dietary fibre intervention and placebo.
- Comparison of blood glucose levels from baseline to the end of intervention between grandmothers, mothers and daughters between dietary fibre intervention and placebo.
- Comparison of blood insulin levels from baseline to the end of intervention between grandmothers, mothers and daughters between dietary fibre intervention and placebo.
- Comparison of gut hormone levels from baseline to the end of intervention between grandmothers, mothers and daughters between dietary fibre intervention and placebo.
- Comparison of blood lipid levels from baseline to the end of intervention between grandmothers, mothers and daughters between dietary fibre intervention and placebo.
- Correlation of 3 days food diary information with gut bacteria production of SCFA among the 2 or 3 generations.

- Correlation of 3 days food diary information with gut bacteria composition among the 2 or 3 generations.
- Correlation of 3 days food diary information with urine metabolic profiles among the 2 or 3 generations.

6. Study methodology:

- Randomised, placebo controlled, double-blinded, cross-over study
- 4 weeks intervention (dietary fibre/placebo) 4 weeks wash-out 4 weeks intervention (opposite arm of intervention)

7. Intervention products:

The fibre intervention product will contain in equal proportions inulin, pectin and oat beta-glucan.

The placebo product will contain cellulose.

The intervention products will be sourced from Nestlé.

The fibre intervention and placebo products will be powders stored in sachets that will look identical and identically-packaged and participants will be able to add them to and mix them with their meals. The amount of intervention taken daily will be increased gradually (see below) to allow participants to adapt to the increased intake of dietary fibre and reduce the likelihood of gastrointestinal discomfort.

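### No test named for fibre versus placebo has a family term, so the error rate and interval for the average fibre effect over 20-30 women from 10 families are uncontrolled

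*Combined protocol and SAP*

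**What the plan says.** Section 6 gives the design as "Randomised, placebo controlled, double-blinded, cross-over study", so each woman who completes contributes one fibre-minus-placebo difference. Section 8 sets the sample at "10 duos or trios (20-30 participants) females", and eligible groups must be "in direct descent and from the same family". The same section says that "statistical power calculation is not possible".

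Section 1 sets out this question for the study: "determine if there is a transgenerational similarity in gut microbiome composition, metabolic profiles and clinical outcomes in response to 4-week high intake of dietary fibres". Placebo is the comparator there. Section 2 hypothesises a larger short-chain fatty acid (SCFA) response in the older generation than in the younger.

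Section 11 says that tests such as ANOVA and "t-tests (paired and unpaired) will be used to compare different groups: study participants groups, dietary fibre groups and placebo groups". For SCFA it adds "Data from placebo and dietary fibre intervention will be compared. Significance levels will be p<0.05". It gives linear models a different task: "linear models will be used to analyse the relationship between gut bacteria taxa, short-chain fatty acids levels, metabolites levels, food diary information and demographics". Sections 11 and 12 mention no family term, random effect, cluster-robust error or family-level summary. Section 7 speaks of randomising participants to product order and does not say whether relatives share an order.

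**The concern.** Women are recruited by family, so there are 10 independent sampling units, not 20 to 30. The best option among the named tests for fibre versus placebo is a t-test paired within woman. Pairing removes each woman's own level, including any level she shares with her relatives. It does not remove a shared response to fibre. If relatives' differences move together, a test that treats them as unrelated overstates the information in the data.

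At stake are the p-value and the interval for the average fibre effect over all women, for SCFA and for every other outcome compared between products. The plan treats familial similarity of response as an open question, so its product comparison should not depend on that similarity being zero.

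The point is limited to this pooled comparison. For the between-generation contrast, positive family correlation makes an unpaired test conservative, which is a separate matter.

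**Working it through.** **Inputs.** From Section 8: 10 families of m = 2 or 3, so 10 × 2 = 20 or 10 × 3 = 30 women, which reproduces the stated range. There is no power figure to reproduce. From Section 11: significance level 0.05; sidedness is not stated, and two-sided is assumed. Assumed, because the documents give no value: the family ICC (ρ) of the fibre-minus-placebo difference, from 0.05 to 0.5.

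**Step 1: no generation difference, mean effect zero.** The design effect is DE = 1 + (m − 1)ρ. The effective number of women is 10m/DE, and the true standard error is √DE times the naive one. The true two-sided level is approximately 2Φ(−1.96/√DE). The last column is from simulation of the pooled paired t-test.

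| Families | ρ | DE | Effective n | √DE | Formula | Simulated |
|---|---|---|---|---|---|---|
| 10 duos | 0.05 | 1.05 | 19.0 | 1.025 | 5.6% | 5.6% |
| | 0.1 | 1.1 | 18.2 | 1.049 | 6.2% | 6.1% |
| | 0.3 | 1.3 | 15.4 | 1.140 | 8.6% | 8.5% |
| | 0.5 | 1.5 | 13.3 | 1.225 | 11.0% | 11.3% |
| 10 trios | 0.05 | 1.1 | 27.3 | 1.049 | 6.2% | 6.1% |
| | 0.1 | 1.2 | 25.0 | 1.095 | 7.4% | 7.2% |
| | 0.3 | 1.6 | 18.8 | 1.265 | 12.1% | 12.2% |
| | 0.5 | 2.0 | 15.0 | 1.414 | 16.6% | 17.2% |

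A t-test on the 10 family means stays at about 5% throughout. A mixture of duos and trios lies between the two blocks.

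**Step 2: generations differ, generation not fitted.** Shift the oldest and youngest women in opposite directions from the mean, in units of the SD of the difference. The unmodelled spread enlarges the naive standard error. At ρ = 0.3, a shift of 0.5 SD gives about 5.3% (duos) and 9.5% (trios). A shift of 1 SD gives about 1.3% and 4.5%, which is conservative.

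**Step 3: generations differ, generation fitted, family omitted.** The offset in step 2 disappears. With a 1 SD shift, the level is about 8% (duos) and 12% (trios) at ρ = 0.3, and about 11% and 16% at ρ = 0.5. Family means again stay at about 5%.

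**Step 4: strict null, no effect in any woman.** Here ρ is the correlation of relatives' period differences, from 0.1 to 0.5. With order drawn independently for each woman, the pooled test stays at 5.0%. With one order per family, it is 6.2-11.3% (duos) and 7.3-17.2% (trios).

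**The case against.** A reader might infer that the plan expects relatives to respond alike, and that the fibre p-value is therefore too small. The documents do not support this.

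- Section 1 poses similarity as a question, and Section 2 hypothesises that generations differ in SCFA response. Similarity after allowing for generation could coexist with that hypothesis, but the plan does not assume it. No ICC is given, and at 0.05 the inflation is only about one percentage point.
- Under the plan's own hypothesis, a pooled t-test that ignores generation may be conservative (step 2).
- If order is independent per woman, the test of no effect in anyone is valid (step 4).
- The plan never commits to a paired t-test over all women. Its list of tests is introduced as examples, and its SCFA sentence on t-tests and ANOVA concerns differences between generations.
- This is an exploratory pilot, so no confirmatory claim rests on this p-value.

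All of this stands as a limit on the claim. It does not remove it. The offset from generation differences is accidental and goes once generation is fitted, which is natural here because the primary outcome compares generations. Validity under the strict null does not extend to the interval for the average effect when responses cluster by family, and it is lost even for the test if relatives share an order. A pilot that reports significance at 0.05 still needs a test whose level is known.

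**Conclusion.** The point holds in conditional form. The plan recruits 10 families and names no method for the product comparison that recognises them, so the error rate and interval for the average fibre effect are uncontrolled. With positive family correlation of the differences, and with generation either fitted or without effect, the true level is about 5.5-11% for duos and 6-17% for trios over assumed ICCs of 0.05 to 0.5. With generation effects left unmodelled, it can fall below 5%.

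The documents do not settle which case applies. It depends on the ICC, the size of the generation difference, the mix of duos and trios, and whether relatives share an order. The conclusion is that the level is unknown and avoidably so, not that a specified test gives a wrong p-value. It should be corrected before analysis.

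**What to change.** For each fibre-versus-placebo comparison across generations, compute each woman's fibre-minus-placebo difference. Fit a linear mixed model with generation and sequence as fixed effects (sequence removes the period effect) and family as a random intercept, using small-sample degrees of freedom. Report the average fibre effect with the interval from that model, and say how generations are weighted in the average.

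The simpler alternative is to average the differences within family and test the 10 family means. It is also a useful check: with only 10 families the estimated family variance may be zero, and the mixed model then returns the naive standard error. The mixed model copes better with families of unequal size, which will arise from mixing duos and trios and because Section 12 lets relatives continue after one woman withdraws.

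State in Section 7 whether order is randomised per woman or per family.

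The cost is a few sentences and one extra model term in R, which the plan already names. Where relatives do respond alike, the interval widens: by a factor of about √2 = 1.41 for trios at an ICC of 0.5 (effective sample 15 of 30 women), but only about 1.05 at an ICC of 0.05, before the small further loss from fewer degrees of freedom.
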